Joint PASS:	If applicable, insert <yes> or <no></no></yes>		
Research question and objectives:	Evaluate clinical outcomes (specifically cardiovascular outcomes like hospitalization for heart failure), and healthcare cost and resource utilization, among patients on empagliflozin as monotherapy or as an add-on therapy to metformin versus patients on sulfonylureas as an add-on therapy to metformin, in patients with T2D and CVD.		
Country(-ies) of study:	United States		
Author:	[name], [contact] and [name], [contact]		
Marketing authorisation holder(s):	< Name, address and contact details of the marketing authorisation holder(s)>		
In case of PASS, add: MAH contact person:	In case of PASS, insert <name contact="" for="" of="" pass
protocol submission (if this a joint PASS, only one person should be mentioned)></name>		
In case of PASS, add: <eu-qppv:></eu-qppv:>	In case of PASS, insert <name and="" contact="" delegate="" details="" eu-qppv="" her="" his="" of="" or="" the=""></name>		
In case of PASS, add: <signature eu-
QPPV:></signature>	In case of PASS, insert <the electronically="" eu-qppv="" is="" of="" provided="" signature="" the=""></the>		
Date:	6/1/2021		
Page 1 of 36			
Proprietary confidential information © 2021 Boehringer Ingelheim Group of companies. All rights reserved.			

This document may not - in full or in part - be passed on, reproduced, published or otherwise used without prior written permission

2. LIST OF ABBREVIATIONS

ADR	Adverse Drug Reaction
AE	Adverse Event
AESI	Adverse Event of Special interest
CA	Competent Authority
CCDS	Company Core Data Sheet
CI	Confidence Interval
CML	Local Clinical Monitor
CRA	Clinical Research Associate
CRF	Case Report Form
CTCAE	Common Terminology Criteria for Adverse Events
CTP	Clinical Trial Protocol
CVD	Cardiovascular Disease
eCRF	Electronic Case Report Form
ENCePP	European Network of Centres for Pharmacoepidemiology and
	Pharmacovigilance
FDA	Food and Drug Administration
GCP	Good Clinical Practice
GEP	Good Epidemiological Practice
GPP	Good Pharmacoepidemiology Practice
GVP	Good Pharmacovigilance Practices
HCRU	Healthcare Cost and Resource Utilization
HHF	Hospitalization from Heart Failure
IB	Investigator's Brochure
IEC	Independent Ethics Committee
IRB	Institutional Review Board
MAH	Marketing Authorization Holder
MedDRA	Medical Dictionary for Regulatory Activities
NIS	Non-Interventional Study
PASS	Post-Authorization Safety Study
SAE	Serious Adverse Event
T2D	Type 2 Diabetes

Adapt and complete as appropriate

3. RESPONSIBLE PARTIES

<List of all main responsible parties including the BI NIS lead, the principal investigator, a coordinating investigator for each country in which the study is to be performed (if applies), study site(s)/data source(s) and other relevant study sites must be listed. Contact details and the list of all investigators can be kept in a stand-alone document to be listed in Annex 1 and to be available upon request.

In case of a Joint PASS, any sharing of responsibilities (e.g. for management of adverse events) or distribution of tasks between marketing authorisation holders and other responsible parties must be mentioned in this section. Contact persons for each marketing authorisation holder must be mentioned.>

4. ABSTRACT

The abstract will be disclosed per the NIS SOP, if applicable, so must provide the appropriate level of detail.

BOEHRINGER INGELHEIM Group of Companies

NIS Protocol Template

Name of company:			
Boehringer Ingelheim			
Name of finished medicinal product: If applicable, list <centrally- authorised medicinal product(s) subject to the study.></centrally- 			
Name of active ingredient: List <pharmacotherapeutic< i=""> group(s){ACT codes} and active substance(s) subject to the study></pharmacotherapeutic<>			
Protocol date:	Study	Version/Revision:	Version/Revision date:
1 June 2021	number:		
Title of study:	Clinical and economic impact of 2^{nd} line initiation of empagliflozin after metformin, as compared to 2^{nd} line initiation of sulfonylurea after metformin in patients with type 2 diabetes and cardiovascular disease.		
Rationale and background:	There are no studies comparing the real-world clinical and economic outcomes of patients prescribed empagliflozin as an add-on therapy to metformin versus patients prescribed sulfonylureas as an add-on therapy to metformin. Given the known benefits of empagliflozin in the T2D population and among those with underlying CVD, understanding the current patterns of care and outcomes is important to establish the potential value of increasing use and earlier access to empagliflozin in this high-risk population.		

NIS Protocol Template

Research question	Provide a clear statement of the objective(s) of the study, i.e. describe what
and objectives:	the study aims to investigate; ideally, should not exceed 3 sentences.
	We will evaluate clinical outcomes (specifically cardiovascular outcomes like hospitalization for heart failure), and healthcare cost, and resource utilization, among patients on empagliflozin as an add-on therapy to metformin versus patients on sulfonylureas as an add-on therapy to metformin in patients with T2D and CVD. Our primary objective is to compare incidence of HHF between the two aforementioned patient populations. The secondary outcomes are comparison of all-cause HCRU outcomes: hospitalizations, emergency department (ED) visits, length of stay, number of filled drugs, outpatient visits and all-cause costs: total cost of care, divided by medical (inpatient costs, outpatient costs, emergency costs) and pharmacy costs (all reported in Per Patient Per Month (PPPM) costs) As exploratory analysis 2 point MACE, a composite outcome of myocardial infarction (MI), stroke, or coronary revascularization.
	For disclosure purposes: Brief Summary (Purpose): Short description of the protocol intended for the lay public. Include a brief statement of the study hypothesis. (Limit: 5000 characters)
	Given the known benefits of empagliflozin in the T2D population and among those with underlying CVD, understanding the current patterns of care and outcomes is important to establish the potential value of increasing use and earlier access to empagliflozin in this high-risk population. This protocol outlines a non-interventional study using existing data that will compare the clinical and economic outcomes among patients on empagliflozin as an add-on therapy to metformin versus patients on sulfonylureas as an add-on therapy to metformin, in patients with T2D and CVD. This study will utilize IQVIA's Real-World Data (RWD) Adjudicated Claims Database (formerly known as PharMetrics Plus) to construct its analytic dataset. Propensity-score matching will be applied to minimize risk of confounding relationships in the dataset that result from any differences between patients of the two different prescribed medications.
Study design:	This study will be a non-interventional study using existing data from January 1, 2014 to the date of the latest available data from IQVIA (detailed below). Data available after March 31, 2020 will not be used due to the potential confounding events of coronavirus.
	The study will analyze the clinical and economic effect of empagliflozin in T2D patients with CVD. Empagliflozin initiators as an add-on therapy to metformin, comprise the treatment population. Patients initiating sulfonylureas as add-on to metformin comprise the control population.

Population:	IQVIA's claims database is composed of more than 190 million unique enrollees from national and sub-national health plans and self-insured employer groups from 2006 to the present. The database is considered representative of the gender and age demographics of the insured United States population.		
	Inclusion criteria:		
	• Prevalent metformin use + initiation of empagliflozin OR prevalent metformin use + initiation of a sulfonylurea		
	• ≥ 18 years of age at index date during study observation		
	• ≥1 inpatient and/or ≥ 2 outpatient claims denoting T2D diagnosis (in any position) in the 12 months prior to index date (Diagnosis codes available in the appendix Error! Reference source not found.)		
	• ≥1 inpatient and/or ≥2 outpatient claims denoting CVD (in any position) diagnosis in the 12 months prior to index date (Diagnosis codes available in the additional workbooks "ICD 9 Dx Codes.xlsx" and "ICD 10 Dx Codes.xlsx")		
	• ≥12 months of no exposure to T2D medications in the pre-index period (excluding metformin in both arms)		
	• ≥ 2 months post-index date		
	• ≥ 12 months of continuous enrollment prior to index date		
	Exclusion criteria:		
	• Diagnosis of Type 1 Diabetes, secondary, or gestational diabetes in the 12 months prior to index date (Diagnosis codes available in the additional workbooks "ICD 9 Dx Codes.xlsx" and "ICD 10 Dx Codes.xlsx"))		
	• Diagnosis of severe comorbidities including malignancy, end-stage renal disease, human immunodeficiency virus, Hepatitis C infection, or organ transplant in the 12 months prior to index date (Diagnosis codes available in the additional workbooks "ICD 9 Dx Codes.xlsx" and "ICD 10 Dx Codes.xlsx")		
	• Admission to nursing home in the 12 months prior to index date		

Variables:	Exposure:		
	 Treatment with Empagliflozin as add-on to 		
	metformin versus Treatment with Sulfonylurea as		
	add-on to metformin		
	Baseline Characteristics (Covariates):		
	• Demographics		
	• E.g. Age, sex, geographic identifier, and time-of-entry indicator		
	 Calendar time of cohort entry (in quarters and days) 		
	 Comorbidities/previous health events 		
	 E.g. Ischemic heart disease, hypertension, hyperlipidemia, chronic kidney disease, ischaemic or haemorrhagic stroke, peripheral arterial disease or surgery, oedema 		
	 Diabetes-related complications, 		
	 E.g. Diabetic neuropathy, diabetic retinopathy, hospitalized hypoglycemia 		
	 Use of diabetes drugs 		
	 Length of metformin use 		
	 Use of other medications 		
	 E.g. Angiotensin converting enzyme inhibitors, Beta-blockers, calcium-channel blockers 		
	 Lifestyle factors 		
	• E.g. Obesity, Overweight, smoker		
	 Previous healthcare utilization 		
	 E.g. Previous coronary revascularization, Endocrinologist visit within prior 30 days, Cardiologist visit within prior 30 days, etc. 		
	Outcomes:		
	Primary outcome		
	 First hospitalization for congestive heart failure (HHF) (we will first analyze this by looking at diagnosis code in any position, we will then run the analysis considering diagnosis coding in either the principal or secondary position). 		
	Secondary outcomes		
	 Healthcare utilization outcomes: hospitalizations, emergency department (ED) visits, length of stay, number of filled drugs, outpatient visits 		

	 All cause cost outcomes: Total cost of care, divided by medical (inpatient costs, outpatient costs, emergency costs) and pharmacy costs (all reported in Per Patient Per Month (PPPM) costs) Exploratory outcome Effectiveness outcomes: 2 point MACE as a Composite Score of myocardial infarction, stroke, or coronary revascularization 	
Data sources:	IQVIA's Real-World Data (RWD) Adjudicated Claims Database (formerly known as PharMetrics Plus)	
Study size:	See Study Size section below for detailed descripted of power calculations. Our estimation corresponds to a minimum and maximum number of events (HHF in both cohorts) required for a powered analysis of 169 and 470 total HHF events between both cohorts.	
Data analysis:	Propensity scores will be calculated using the listed covariates (below) and used to construct PSM cohorts, if the post-matching sample size still allows for a powered analysis, or IPTW cohorts if not. Using observed clinical events, we will calculate incidence rates and 95% confidence intervals for PSM (or IPTW) cohorts. We will estimate the hazard ratios and confidence intervals via Cox regression for our primary outcome (HHF). We will also estimate differences in healthcare utilization using incident counts, by performing either Poisson or negative binomial regression. Differences in cost outcomes will be assessed by generalized linear regression using a Gamma family link function. We will also explore instrumental variables that are employed to minimize residual confounding after PSM (or IPTW).	
Milestones:	The database for this analysis will be constructed by March 08, 2021, Data analyses will be complete April 12, 20201. A report of the findings from this study will be complete for review June 7, 2021.	

5. AMENDMENTS AND UPDATES

Write <None> or indicate any substantial amendment and update to the study protocol after the start of data collection in a table as indicated below.

Number	Date	Section of study protocol	Amendment or update	Reason
1	<dd i="" month<=""> YYYY></dd>	<text></text>	<text></text>	<text></text>
2	<dd i="" month<=""> YYYY></dd>	< Text >	< Text >	<text></text>
<n></n>	<dd i="" month<=""> YYYY></dd>	<text></text>	< Text >	<text></text>

6. MILESTONES

Milestone	Planned Date
Execute 3 rd party data agreement	09/15/2020
Precision obtain data for analyses	10/01/2020
Finalize analysis plan	06/07/2021
Construct analytic dataset	07/02/2021
Complete all analyses	07/23/2021
Complete study report	08/27/2021

7. RATIONALE AND BACKGROUND

Approximately 13% of adults in the United States have been diagnosed with diabetes, with approximately 90% of those cases attributable to T2D.¹ Patients with diabetes are at much higher risk for CVD than patients without diabetes, and adults with T2D have a 2-to-4 fold higher risk of cardiovascular morbidity and mortality.² The American Heart Association lists T2D as one of the seven major controllable risk factors for CVD, with glycemic control being a contributing factor to cardiac impairments among patients with T2D.²

Empagliflozin (Jardiance), is a SGLT2i; this therapy was first approved in 2014 for the reduction of HbA1c in patients with T2D, and is available both as monotherapy and as add-on therapy. In 2016 empagliflozin received a new indication for reducing cardiovascular death in patients with T2D and CVD, and a 2020 update to the American Diabetes Association Standards of Care recommends the addition of either SGLT2i or GLP1-RA for patients with pre-existing cardiovascular disease or kidney disease.³ In clinical studies, the rate of death in patients taking empagliflozin vs. placebo has been significantly reduced (3.7%, vs. 5.9%; 38% relative risk reduction; p-value <0.001), as have rates of hospitalization for heart failure (HHF) (2.7% vs. 4.1%; 35% relative risk reduction) and all-cause death (5.7% vs. 8.3%; 32% relative risk reduction; p-value 0.002).⁴ A 2017 real world claims analysis which studied HHF rates of T2D patients starting canagliflozin, dapagliflozin, or empagliflozin (53%, 42%, and 5% of patients, respectively) found a 39% risk reduction in HHF and 51% risk reduction in all-cause death versus other glucose reducing drugs.⁵ The overall safety profile of empagliflozin was found to be similar to that of placebo in the EMPA-REG OUTCOME trial.⁶

Though there are few studies on the cost effectiveness of empagliflozin, current literature suggests it is cost effective versus other antihyperglycemic agents (AHA). Real world analysis of the economic impacts of empagliflozin for patients with T2D demonstrates a per member per month (PMPM) reduction in all-cause healthcare costs of \$412 compared to other branded anti-hyperglycemic agents (DPP4-inhibitors, GLP1-agonists, other SGLT2-inhibitors, and

insulins).⁷ These costs differences were largely due to lower all-cause medical costs, with there being only a small (\$31) cost difference between empagliflozin and other AHA pharmacy costs.⁷ This is significant, as the economic cost of diabetes in the United States was estimated at \$237 billion in annual direct costs in 2017, and patients with diabetes have medical expenditures over twice as high as those without diabetes.^{8,9}

Sulfonylureas are a class of antidiabetic medications which work by stimulating insulin release from pancreatic cells, and include the generics chlorpopamide, glyburide, tolazamide, and tolbutamide.¹⁰ There is some evidence suggesting that sulfonylureas are associated with increased risk of cardiovascular events and mortality. In a review of observational studies comparing metformin and sulfonylureas, the relative risk of adverse events was 13% higher in sulfonylureas patients with a ratio of relative risks of 1.13 (95% CI 1.01-1.27), and the relative risk of death was increased by 20% (RRR 1.20, 95% CI 1.07-1.34).¹¹ Of note, a review of the cardiovascular profile of diabetic drugs found multiple studies suggesting a detrimental effect on cardiovascular health in patients treated with sulfonylureas.¹² Direct comparisons of sulfonylureas to empagliflozin are currently not available, but evidence suggests that empagliflozin is well tolerated as add on therapy to patients using metformin plus sulfonylureas.¹³ Comparisons between the cost effectiveness of sulfonylureas and empagliflozin are not currently available, though previous evidence suggests that metformin is more cost effective than sulfonylureas, with one study estimating an increase of \$2,800 over 25 years when glyburdide was used as first line therapy over metformin, while at the same time accumulating 0.17 fewer quality adjusted life year (QALYs).¹⁴

Given the known benefits of empagliflozin in the T2D population and among those with underlying cardiovascular disease, understanding the current patterns of care and outcomes is important to establish the potential value of increasing use and earlier access to empagliflozin in this high-risk population.

This study would also be the first to assess empagliflozin as second-line after metformin versus second-line initiation of sulfonylureas in the United States using the IQVIA commercial claims database to look at clinical and economic outcomes.

8. **RESEARCH QUESTION AND OBJECTIVES**

Evaluate clinical outcomes (specifically cardiovascular outcomes like hospitalization for heart failure), and healthcare cost, and resource utilization, among patients on empagliflozin as an add-on therapy to metformin versus patients on sulfonylureas as an add-on therapy to metformin, in patients with T2D and CVD.

Specifically our objectives are the following

- 1. Primary Objective
 - a. Compare incidence of HHF between the two aforementioned patient populations.
- 2. Secondary Economic Objectives
 - a. Comparisons of HCRU outcomes: hospitalizations, emergency department (ED) visits, length of stay, number of filled drugs, outpatient visits
 - b. Comparisons of all-cause cost outcomes: Total cost of care, divided by medical (inpatient costs, outpatient costs, emergency costs) and pharmacy costs (all reported in Per Patient Per Month (PPPM) costs)
- 3. Exploratory Objective
 - a. Comparisons of 2-Point MACE as a Composite Score of myocardial infarcton, stroke or coronary revascularization

9. **RESEARCH METHODS**

9.1 STUDY DESIGN

This study will be a non-interventional study using existing data from January 1, 2014 to the date of the latest available data from an IQVIA (detailed below) database. Data available after March 31, 2020 will not be used due to the potential confounding events of coronavirus.

The study will analyze the clinical and economic effect of empagliflozin in Type 2 Diabetes (T2D) patients with Cardiovascular Disease (CVD). Empagliflozin initiators, as an add-on to metformin therapy comprise the treatment population. Patients initiating sulfonylureas as an add-on to metformin comprise the control population.

The index date for the empagliflozin add-on therapy arm is defined as the date of initiation of empagliflozin.

Treatment patient: Empagliflozin + Metformin
Control patient: Sulfonylurea + Metformin
 Metformin initiation Index Date = Empagliflozin/Sulfonlurea initiation

Page 16 of 36

The index date for the sulfonylurea add-on therapy control arm in a format parallel to the definition for the empagliflozin add-on therapy treatment arm, i.e., the index date is defined as the date of initiation of sulfonylurea therapy. We will control for exposure time in our propensity score calculations.

Baseline characteristics for all patients as well as their enrollment status will be confirmed using 12 months of claims data prior to the index date. Cardiovascular events, healthcare utilization, and its associated costs will be observed from the index date until the end of the study period. Outcomes and the associated costs will be monitored and then compared between cases and controls using inverse probability treatment weighting (IPTW), or, as sample size allows, propensity score matching.

*Monitoring period can also be ended by one of the events described in the data analysis section below

For this study, index date selection period will be from 01/01/2015 to 1/31/2020. Follow-up up period for patients not meeting any of the stopping criteria mentioned below will extend until 3/31/2020.

Finally, starting with the initiation of treatment, we observe patient outcomes until one of the following stopping criteria occur:

- discontinuation (defined as a gap in sulfonylurea, empagliflozin, or metformin of >30 days between fills) or switch or addition of a drug in the comparator and/or other antihyperglycemic agents class
- occurrence(s) of an outcome of interest
- nursing home admission
- healthcare plan disenrollment
- end of the study period

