9.2.2 Study population

Inclusion criteria:

- Prevalent metformin use + initiation of empagliflozin OR prevalent metformin use + initiation of a sulfonylurea
- ≥ 18 years of age at index date during study observation
- ≥1 inpatient and/or ≥ 2 outpatient claims denoting T2D diagnosis (in any position) in the 12 months prior to index date (Diagnosis codes available in the appendix Error! Reference source not found.)
- ≥1 inpatient and/or ≥2 outpatient claims denoting CVD (in any position) diagnosis in the 12 months prior to index date (Diagnosis codes available in the additional workbooks "ICD 9 Dx Codes.xlsx" and "ICD 10 Dx Codes.xlsx")
- ≥ 2 months post-index date
- ≥12 months of no exposure to T2D medications in the pre-index period (excluding metformin in both arms)
- ≥ 12 months of continuous enrollment prior to index date

Exclusion criteria:

- Diagnosis of Type 1 Diabetes, secondary, or gestational diabetes in the 12 months prior to index date (Diagnosis codes available in the additional workbooks "ICD 9 Dx Codes.xlsx" and "ICD 10 Dx Codes.xlsx"))
- Diagnosis of severe comorbidities including malignancy, end-stage renal disease, human immunodeficiency virus, Hepatitis C infection, or organ transplant in the 12 months prior to index date (Diagnosis codes available in the additional workbooks "ICD 9 Dx Codes.xlsx" and "ICD 10 Dx Codes.xlsx")
- Admission to nursing home in the 12 months prior to index date

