9.3.2 Outcomes

9.3.2.1 Primary outcomes

Primary outcome

• First hospitalization for congestive heart failure (HHF) (we will first analyze this by looking at diagnosis code in any position, we will then run the analysis considering diagnosis coding in either the principal or secondary position).

The primary scope of the analysis will be limited to the primary outcome (hospitalization for HF), for which the study will be powered for, and limited to HCRU and cost outcomes. For all exploratory effectiveness outcomes outlined above, we will first examine the number of events, and incidence rate of the events in the follow-up for the unmatched cohort, before performing the final analysis, to evaluate feasibility of inclusion of these exploratory outcomes.

Clinical outcomes will be identified by occurrence of a combination of the ICD 9/10 for the respective condition and HCSPCS code. See additional workbooks "ICD 9 Dx Codes.xlsx" and "ICD 10 Dx Codes.xlsx" and "HCPSC codes.xlsx" for a detailed list of relevant ICD 9/10 codes and HCSPCS codes, respectively.

Effectiveness Outcome	Metformin + Sulfonylurea(IR)	Metformin + Empagliflozin (IR)	Hazard Ratio (95% CI)
HHF			
MACE			
Myocardial infarction			
Stroke			
Coronary revascularization			
All-cause death			

See sample results for the propensity score-matched population below:

Utilization Outcome (12 months post index date)	Metformin + Sulfonylurea (IR)	Metformin + Empagliflozin (IR)	Coefficient (95% CI)	P value
Hospitalizations				
LOS				
ED visits				
Outpatient visits				
Drug orders				
Total care costs				
Medical costs				

Pharmacy costs		
2		

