9.7 DATA ANALYSIS

9.7.1 Main analysis

As described above starting with the initiation of treatment, we observe patient outcomes until one of:

- discontinuation or switch or addition of a drug in the comparator and/or other antihyperglycemic agents class
- occurrence(s) of an outcome of interest
- nursing home admission

- healthcare plan disenrollment
- exposure to other diabetes medications
- end of the study period

Step 1: Create the matched sample

There are many variants of propensity score matching. In the simplest version, individuals in the case group are matched 1:1 with individuals in the set of candidate controls, on the basis of similarity (minimized difference) of the propensity score, using a list-wise matching process (a list-wise matching process is one in which first a match for empagliflozin add-on patient 1 is found, then a match for case member 2, iterating to finding a match case group member N at the end of the matching procedure). In K-nearest neighbors matching, case group members are matched to the K members of the candidate set of controls (where K is a small positive number such as 2, 3 or 4), again based on minimized difference in propensity score. This method can be used if the initial data inspection determines that a larger sample size is required. It can improve the precision of estimates, but may result in additional bias due to poorer matches on average. In caliper matching (which may be applied to either nearest neighbor or K-nearest neighbor variants), individuals are selected for inclusion if their propensity score distance from the matching candidate is less than some caliper parameter, c (for estimating means or risk differences, often caliper width equaling 0.2 of the standard deviation of the logit of propensity score is used for estimating risk differences or differences in means). If no acceptable match is found within the caliper, the case is dropped. Caliper matching may be required if it is necessary to ensure that all matches meet some minimally acceptable threshold for match quality; however, it may further reduce the generalizability of study findings by dropping large numbers of cases.

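### Follow-up starts on the day of the first fill itself, so a same-day admission with a heart failure code counts as a first HHF at time zero; the size and direction of the bias are unknown

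*Protocol*

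**What the plan says.** The start of follow-up is fixed in two sections of the protocol.

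- **Index date (9.1).** "The index date for the empagliflozin add-on therapy arm is defined as the date of initiation of empagliflozin"; the sulfonylurea arm is defined in parallel. Section 9.3 identifies exposure from prescription fills.
- **Baseline (9.1).** Characteristics and enrolment "will be confirmed using 12 months of claims data prior to the index date". Day 0 is therefore not baseline.
- **Outcomes (9.1).** "Cardiovascular events, healthcare utilization, and its associated costs will be observed from the index date until the end of the study period".
- **Same start, restated.** Section 9.1: "starting with the initiation of treatment, we observe patient outcomes until one of the following stopping criteria occur". Section 9.7.1: "starting with the initiation of treatment, we observe patient outcomes until one of". In both lists an outcome of interest is one of the events that end observation.
- **Primary outcome (9.3.2.1).** "First hospitalization for congestive heart failure (HHF) (we will first analyze this by looking at diagnosis code in any position"; a second analysis limits the code to the principal or secondary position.

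No section starts risk on day 1, sets aside same-day admissions, or says whether a stay is dated by admission or by discharge. Heart failure in the past year is a covariate (9.3), not an exclusion (9.2.2). The criterion "≥ 2 months post-index date" in 9.2.2 does not ask for event-free time.

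**The concern.** An admission on the day of the first fill is more plausibly a reason for starting the drug, or a companion of starting it, than a result of it. Under the stated rule it becomes an outcome with no exposure behind it.

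Three things follow from the protocol's own rules:

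1. The patient leaves observation at time zero, so a later HHF on treatment is never counted.
2. Because the first HHF analysis accepts a heart failure code in any position, and everyone enrolled has cardiovascular disease, an admission for another reason with heart failure listed also qualifies.
3. The days and cost of that admission enter hospitalizations, length of stay and inpatient cost.

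The protocol already treats recent admission as a potential confounder, since hospitalization in the prior 30 days is a listed covariate. An admission one day before the fill is adjusted for. The same admission on the fill date is scored as the endpoint. If starts around an admission are more common with one drug than the other, the hazard ratio picks up that difference.

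**Working it through.** **1. What day 0 is.** Baseline ends before the index date and outcomes run from it, so the two windows meet with day 0 on the outcome side. The later statements in 9.1 and 9.7.1 use treatment initiation, which is the same date. The passages agree with one another, so this is a stated rule and not a gap between sections.

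**2. Inputs for an illustration.**

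- HHF rates, section 9.5: 9.4 (empagliflozin) and 14.5 (control) per 1,000 patient-years.
- Empagliflozin patients with any metformin supply, table in 9.5: 461 + 331 + 375 + 801 = 1,968.
- Mean follow-up *t*: not given. Assumed 0.75 years, range 0.5 to 1.5.
- Day-0 heart failure admissions per 1,000 starters, *a* (empagliflozin) and *b* (sulfonylurea): not given. Assumed.

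**3. The plan's own ratio.** 9.4 / 14.5 = 0.648, which agrees with the hazard ratio of 0.65 used in 9.5. The events required there (169, 265 and 470 at control shares of 0.5, 0.8 and 0.9) depend on the hazard ratio, allocation and error rates only, and this point does not change them.

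**4. Expected events at 0.75 years, 1:1 matching.** 1,968 × 0.75 × 9.4/1,000 = 13.9 and 1,968 × 0.75 × 14.5/1,000 = 21.4.

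**5. Adding day-0 events.** They add events and no person-time, so the crude rate ratio is

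(1,968·*t*·9.4 + 1,968·*a*) / (1,968·*t*·14.5 + 1,968·*b*) = (9.4*t* + *a*) / (14.5*t* + *b*).

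The 1,968 cancels. The shift depends on the day-0 shares and on follow-up, not on the number of patients.

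At *t* = 0.75, *a* = *b* = 1: (7.05 + 1) / (10.875 + 1) = 8.05 / 11.875 = 0.678.

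| Day-0 per 1,000 (empa, SU) | *t* = 0.5 | *t* = 0.75 | *t* = 1.0 | *t* = 1.5 |
|---|---|---|---|---|
| 0, 0 | 0.65 | 0.65 | 0.65 | 0.65 |
| 1, 1 | 5.7/8.25 = 0.69 | 8.05/11.875 = 0.68 | 10.4/15.5 = 0.67 | 15.1/22.75 = 0.66 |
| 2, 1 | 6.7/8.25 = 0.81 | 9.05/11.875 = 0.76 | 11.4/15.5 = 0.74 | 16.1/22.75 = 0.71 |
| 1, 3 | 5.7/10.25 = 0.56 | 8.05/13.875 = 0.58 | 10.4/17.5 = 0.59 | 15.1/24.75 = 0.61 |

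Equal shares pull the ratio toward 1; unequal shares can move it either way.

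**6. How strong the assumption is.** If day 0 were like any other day, the shares would be 9.4/365 = 0.026 and 14.5/365 = 0.040 per 1,000, in the same proportion as the rates, and the ratio would not move. One per 1,000 is about 39 and 25 times those daily rates (1/0.0258 and 1/0.0397). The bias exists only to the extent that admissions cluster on the day of the first fill. With *a* = *b* = 0.1 it is negligible: 7.15 / 10.975 = 0.651.

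**7. Against random error.** With 13.9 and 21.4 events the standard error of the log ratio is √(1/13.9 + 1/21.4) = 0.34. The equal-share shift is ln(0.678/0.648) = 0.045, about 0.13 standard errors.

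These are crude rate ratios, not Cox estimates. Some Cox software drops records with time zero, so without a rule the result may also depend on the program.

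**The case against.** The strongest reply is that counting from the index date is ordinary cohort wording, and that day-0 handling and stay dating are programming rules for the analysis plan, which section 6 schedules after this protocol. That would answer a protocol that was silent. This one places baseline before the index date and outcomes from it, and an analysis plan starting risk on day 1 would depart from that text. The date that defines a stay is left open, and on that alone there would be no finding.

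Two stronger readings are tempting and should not be drawn.

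- *A stay already in progress at the first fill is booked to the new drug.* That needs stays to be dated by discharge, which the protocol nowhere says; such a stay began before the index date and can equally be read as baseline. If a patient is admitted, stays overnight and fills at discharge, the admission date precedes day 0. Under admission dating, only an admission and fill on the same calendar day are affected.
- *The hazard ratio is vulnerable because the empagliflozin arm expects few events.* Step 5 shows that the number of patients cancels: for given day-0 shares the shift is the same in a far larger cohort. Few events make the estimate imprecise, which is a separate matter that 9.5 partly addresses by making the analysis conditional on accrued events.

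It is also fair that the covariates (recent hospitalization, heart failure, recent cardiologist visits) should balance some of the difference in who starts around an admission. They do not remove a day-0 event from the outcome.

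**Conclusion.** The point holds in a limited form. As written, sections 9.1 and 9.7.1 count an admission on the day of the first fill, with a heart failure code in any position, as a first HHF at time zero. That admission cannot credibly be attributed to the drug, it ends the patient's observation, and its days and cost enter the secondary outcomes.

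The documents give neither the number of such admissions nor the mean follow-up, so the size and direction of the bias are unknown. The move from 0.65 to about 0.68 rests on two assumptions: 0.75 years' mean follow-up and one day-0 event per 1,000 starters in each arm. The larger shifts in the table also need the arms to differ in a way for which the documents offer no evidence. The case for changing the rule is that the better rule is nearly free, not that a large bias has been shown.

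**What to change.** Change the same sentence in 9.1 and 9.7.1, and add the supporting definitions:

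- Time at risk for HHF, MACE, hospitalizations, length of stay and medical costs starts on the day after the index date.
- Hospital stays are dated by admission.
- Stays admitted on or before the index date do not count toward outcomes, including their days and cost. For these stays the baseline covariate window includes the index date.
- The index fill stays in pharmacy cost, and the PPPM definition says so.
- The number of index-day admissions with a heart failure code is reported by arm, so the effect of the rule can be seen.

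This takes a few sentences and a date condition in the programming. It costs a few counted events. It also makes the medical cost window one day shorter at its start than the pharmacy window, which is why the PPPM definition must state it.
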